A decreased level of VEGF and PIGF free form has been observed that has been attributed to their blockade by the increased level of sFlt-1 in pre-eclamptic women (29,41,42). Indeed, the introduction of sFlt-1 to a pregnant rat led to hypertension and proteinuria similar to that seen in PET women (42). Furthermore, an altered ratio of serum PIGF/sFlt-1 has been found to be associated with PET diagnosis and disease severity (43–46). Indeed, there is now a drive to use this ratio in screening women at risk of PET but most of the data were generated in late pregnancy rather than in early pregnancy – a time when interventions have been shown to have maximum impact (46). It would seem from this greater understanding of the underlying physiological changes in women that develop PET that any interventions that have the potential to alter this milieu are more likely to be successful.

Very recently a double-blind, placebo-controlled trial, that randomly assigned pregnant women without diabetes who had a body-mass index of more than 35 to receive metformin, at a dose of 3.0 g per day, or placebo (225 women in each group) from 12 to 18 weeks of gestation until delivery showed a significant reduction in the incidence of PET in those who received metformin (47). Since metformin is now frequently prescribed to obese type II diabetic women and gestational diabetics with poor glycemic control on diet, it is hypothesized in those at risk of PET, metformin will not only reduce the incidence of PET but will modify the PIGF/s-Flt-1 ratio in favor of normal pregnancies.

2. Study aims and goals

Aim 1: To investigate whether the administration of metformin to women at high risk of pre-eclampsia will reduce the incidence.

Aim 2: To determine accuracy of the ratio of PIGF/sFlt-1 in predicting PET and the effect of metformin on this ratio

Aim 3: To study the molecular mechanisms and signaling pathways associated with increased levels of sFlt-1 and PET

3. Objectives of this study

Aim 1: To investigate whether the administration of metformin to women at high risk of pre-eclampsia will reduce the incidence.

The objectives under this aim will include

1. A comparison of the incidence of pre-eclampsia and its severity in women receiving metformin versus standard care,
2. A comparison of the GA at delivery, maternal and fetal outcomes in those receiving Metformin versus standard care,
3. A comparison of the timing of onset of PET between the two groups and

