Systolic blood pressure of 160 mm Hg or more, or diastolic blood pressure of 110 mm Hg or more on two occasions at least 4 hours apart (unless antihypertensive therapy is initiated before this time), Thrombocytopenia (platelet count less than $100,000 * 10^9/L$), Impaired liver function as indicated by abnormally elevated blood concentrations of liver enzymes (to twice the upper limit normal concentration), and severe persistent right upper quadrant or epigastric pain unresponsive to medication and not accounted for by alternative diagnoses, Renal insufficiency (serum creatinine concentration more than 1.1 mg/dL or a doubling of the serum creatinine concentration in the absence of other renal disease), Pulmonary edema
 New-onset headache unresponsive to medication and not accounted for by alternative diagnoses, Visual disturbances

Study population:

Patient characteristics:

Participants who will be included in this study are pregnant women who are at high risk for developing pre-eclampsia as defined by the ACOG practice bulletin (for review (67)).

Inclusion criteria:

To be eligible to be included in the study, a woman has to have all of the following; Confirmed y, gestational age $< 12^{+0}$ weeks, live fetus at time of booking ultrasound scan

(between 11⁺⁰ and 13⁺⁶ weeks of gestation), and to be considered as high risk of preeclampsia. According to ACOG (67), pregnant women are considered high risk of preeclampsia if they showed at least one of the following; History of preeclampsia, especially when accompanied by an adverse outcome, Multifetal gestation, chronic hypertension, Type 1 or 2 diabetes, Renal disease, Autoimmune disease (ie, systemic lupus erythematosus, the antiphospholipid syndrome), OR more than one of the following: Nulliparity, Obesity (body mass index greater than 30), Family history of preeclampsia (mother or sister), Sociodemographic characteristics (African American race, low socioeconomic status), Age 35 years or older, Personal history factors (eg, low birth weight or small for gestational age, previous adverse pregnancy outcome, more than 10-year pregnancy interval)

Exclusion criteria:

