Age under 18 years, hyperemesis gravidarum, unable to sign the consent form, type 1 or 2 diabetes mellitus, early gestational diabetes, auto-immune disease, fetal abnormality identified at time of scanning (between 11⁺⁰ and 13⁺⁶ weeks of gestation), bleeding disorder, peptic ulcer, hypersensitivity to aspirin or metformin, long use of NSAIDS before initiation of intervention, contraindication to metformin or aspirin and participation in another concurrent trial.

Study sites:

The study will be conducted at the Women Wellness and Research Center (WWRC), Doha, Qatar. Patient will be identified from three Primary Health Centers. There will, however, will be very few volunteers who will have all their visits and tests done at the WWRC with the health center facilitating their identification only.

Study methods:

Patient identification and randomization

If the primary physician in the Primary Health Center or the main center identifies a potential candidate for the study based on the inclusion and exclusion criteria, he/she will inform the patient about the study and document her willingness to participate in the study in the electronic medical record to avoid cold calling and according to HIPAA recommendations. The investigator of the respective site will then be contacted through email by the primary physician.

the patient will be contacted by the study investigator and arrange an appointment in the WWRC to inform her about the study and if she accepted to participate, give her the patient information leaflet (PIL) and then obtain informed consent once all her questions have been answered.

Each center has one coordinator, who will be responsible in conjunction with the investigator for recruitment, clinical interviews, determining eligibility and obtaining signed informed consent forms. After successful screening, eligible pregnant women will be randomly assigned to either intervention or control group. Random sized blocks of 4 or 6 will be computer generated with 1:2 ratio.

Sample isolation and laboratory studies (appendix 2):

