each visit or telephone call. Furthermore, to increase patient medication adherence, a reminder SMS will be send as well as three telephone calls to individual patient on regular basis. Adverse drug reaction (ADRs) will be reported using [name] Medical Corporation ADR form (Appendix 7) to both DSMC and MRC when they occur, however, serious ADRs will be reported within 48 hours by the study PI.

6. Sample size and calculation

Our sample size calculation was based on Syngelaki A. et al. (2016) findings. In this study, obese patient where either randomized to metformin or placebo to see the effect on neonatal birth weight. As a secondary outcome, metformin use was associated with 76% reduction in PET (3% versus 11.3% respectively, OR 0.24, 95% CI 0.10 – 0.61, $P = 0.001$).

We expect that for a study power of 80% and to detect a reduction at a level of 5% significance, with considering above outcome estimates it is approximately estimated to be 172 patients in each arm, for a total of 344 in both group based on 1:1 ratio. Allowing for a maximum 20% dropout, we estimate that 414 patients would need to undergo randomization, to give 207 patients in each group.

7. Data collection methods and procedure

These will be at baseline, in the second and again in the third trimesters. The data to be collected include patient clinical information, blood sample and placental tissue (appendix 5). At each study visit 5 ml maternal venous whole blood will be collected by a laboratory phlebotomist or a nurse (one at baseline, and one at each following trimester/visit and admission/s, see appendix 2) for all included subjects. The blood sample will be used for measuring blood markers for aim 2 and stored for future DNA/RNA analysis for aim 3. In addition, placental tissue will be collected and stored for future DNA/RNA analysis. In brief:

- (a) Baseline Data (Week 11⁺⁰ to 13⁺⁶): Patient sociodemographic data including age and ethnicity, Obstetrical, medical, surgical and medication history, current pregnancy information, CBC, as routinely done and study biomarkers of LFT, serum creatinine, sFlt-1, VEGF and PIGF.
- (b) Second (week 19⁺⁰ to 24⁺⁶) and third trimester visits (week 32⁺⁰ to 34⁺⁶): At these visits the same data collected at baseline will be obtained. If the patient is, however, admitted for pre-eclampsia before the third visit, the collection will follow the pre-eclampsia diagnosis at admission including treatment offered, length of hospitalization and management.

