- (c) At delivery data to be collected will include gestational age at admission, vital signs, indication for delivery, type of delivery, compliance with protocol, blood for CBC, LFT, and the biomarkers of interest. Post-delivery, discharge vitals, antihypertensive treatment on discharge will be collected.

(d) Exit interview: patient will be called to check for any relevant ADR.

8. Data Management and Analysis plan

Data management:

Upon randomization, research coordinators will be responsible for data collection using approved CRFs. To maintain patient confidentiality, study document such as signed informed consent, and CRFs will be stored in locked cabinets, excel file containing patient identifiable information will be password protected, and all data including patient clinical information and research laboratory results will be entered into the clinical trial management software using patient generated study ID number.

Data analysis:

Descriptive data: Numerical data will be presented as mean and standard deviation where normally distributed or median and range where it's not normally distributed. Categorical data will be presented as frequency and percentages. The percentage of women developed PET will be compared between the intervention and control group using chi square test.

Quantitative data between two arms will be analyzed using either "Unpaired t test or Mann Whitney U test depending on normality of the data distribution". Also, outcomes measured at different time points should be statistically analyzed both within and between groups using repeated measure ANOVA statistical method followed by appropriate multiple comparison tests. All P values presented will be two-tailed. A multivariate logistic regression will be employed to assess the association between metformin use and PET adjusting for confounding factors such as patient demographics (age, GA at delivery, history of risk factors of PET\mentioned above) and co-morbidities such as DM, the dose of metformin, the need to use of antihypertensive drugs, including duration of treatment and any other medications. P values <0.05 will be considered as statistically significant. All Statistical analyses will be done using statistical packages SPSS 22.0 (SPSS Inc. Chicago, IL) and Epi-info (Centers for Disease Control and Prevention, Atlanta, GA) software.

9. Anticipated results and evaluation criteria

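### The between-arm test for gestational age at delivery ignores plurality; stratifying by it is a free improvement, with a gain that depends on an unstated multifetal share

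*SAP*

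**What the plan says.** The relevant statements are spread over four sections of the SAP.

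- **Outcome.** Section 3, Aim 1, objective 2: "A comparison of the GA at delivery, maternal and fetal outcomes in those receiving Metformin versus standard care".
- **Entry.** The inclusion criteria in section 5 list conditions that each qualify a woman on their own, among them "Multifetal gestation, chronic hypertension, Type 1 or 2 diabetes, Renal disease". The exclusion criteria remove diabetes and autoimmune disease but not multifetal pregnancy.
- **Randomisation.** Section 5, patient identification and randomization: "Random sized blocks of 4 or 6 will be computer generated with 1:2 ratio". No stratification factor is named.
- **Test.** Section 8, data analysis, gives quantitative data the "Unpaired t test or Mann Whitney U test depending on normality of the data distribution". Outcomes measured at several time points go to "repeated measure ANOVA statistical method followed by appropriate multiple comparison tests".
- **Adjustment.** The only covariate-adjusted analysis is for pre-eclampsia: "A multivariate logistic regression will be employed to assess the association between metformin use and PET adjusting for confounding factors". The covariates listed there include the woman's risk factors for pre-eclampsia. GA at delivery has no adjusted analysis.

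**The concern.** GA at delivery takes one value per woman, so correlation between babies of the same mother is not the issue here. Multifetal pregnancies can be expected to deliver earlier than singletons. A test that pools the two types counts the gap between them as random noise. Plurality is fixed before randomisation and is visible at the scan at 11+0 to 13+6 weeks, so conditioning on it raises no post-randomisation difficulty. The plan already accepts adjustment for risk factors when the outcome is pre-eclampsia, but provides none for GA at delivery.

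At stake is the power and the width of the confidence interval for a named Aim 1 comparison in a trial whose size was set on a different outcome.

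**Working it through.** **The plan's own figure.** Section 6 takes pre-eclampsia rates of 11.3% and 3%, 80% power and 5% significance, and arrives at 172 per arm. The two-sided formula gives 151 per arm without continuity correction and 174 with it, so 172 is reproduced to within about 1%. It is sized on pre-eclampsia and sets no power target for GA. It is used here only as the number of women per arm.

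**Inputs the SAP does not give (assumptions).** Multifetal share p = 2, 5, 10 and 20%; gap g = 2.7 weeks; true effect of metformin on GA 0.55 week; skewed GA generated as 39.3 − Gamma(shape 1.2, scale 1.4) + N(0, SD 0.7) − 2.7 × multifetal + 0.55 × arm.

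**Within-type variance.** 1.2 × 1.4² + 0.7² = 2.352 + 0.49 = 2.842, so the SD is 1.69 weeks.

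**Share of variance due to plurality.** p(1 − p)g² / [p(1 − p)g² + 2.842], with g² = 7.29. At p = 10%: 0.09 × 7.29 = 0.656, and 0.656 / 3.498 = 18.8%.

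**Power, by simulation at 172 per arm, two-sided 5%:**

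| Multifetal share | Variance due to plurality | Mann-Whitney | Stratified (van Elteren) |
|---|---|---|---|
| 2% | 4.8% | 0.93 | 0.95 |
| 5% | 10.9% | 0.91 | 0.94 |
| 10% | 18.8% | 0.88 | 0.94 |
| 20% | 29.1% | 0.81 | 0.94 |

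Type I error is near 0.05 for both tests.

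**Where chance imbalance sits.** At p = 10%, the standard error of the mean difference is:

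- unadjusted: √(3.498 × 2/172) = 0.202 week;
- adjusted for plurality: √(2.842 × 2/172) = 0.182 week;
- shift due to unequal multifetal numbers alone: 2.7 × √(0.09 × 2/172) = 0.087 week.

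Since 0.182² + 0.087² ≈ 0.202², the imbalance is already inside the unadjusted standard error.

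**Sensitivity.**

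- Normal GA, 3-week gap, SD 2, t test against a linear model with arm and plurality: power rises from 79 to 83% at 5% multifetal, 80 to 87% at 10% and 79 to 90% at 20%.
- Gaps of 2 to 4 weeks, SDs of 1.5 to 3 weeks and shares of 2 to 30%: plurality accounts for 1% to 60% of the variance. A contrast with 80% power unadjusted then has between 80% and 99% when adjusted.
- The 1:2 allocation in section 5, same total of 344, skewed model: 0.87 to 0.90, 0.84 to 0.91 and 0.74 to 0.91 at 5, 10 and 20% multifetal.
- Cost of the extra term in a linear model: one degree of freedom, which moves the t critical value from 1.96692 to 1.96695.

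**The two remedies are not equal.** In the skewed model the linear model with plurality has power of about 0.85. That is below even the unstratified Mann-Whitney test at 10% multifetal or less.

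**The case against.** The strongest reply is that nothing here is wrong. A t or Mann-Whitney test of a randomised comparison is valid without covariates, and the simulations confirm its type I error. GA at delivery is not the outcome that sized the trial, and the SAP presents the trial as groundwork for a larger one. Multifetal gestation is one of many entry routes, so the share could be small and the gain trivial. All of this stands, and it makes the point an improvement in efficiency and not a correction.

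A reader might infer more than the documents support:

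- **That the comparison is biased, or that a chance surplus of twins in one arm is a further harm.** Randomisation makes the unadjusted test valid, and the imbalance is part of its standard error, as shown above.
- **That plurality is a large source of noise in this trial.** The SAP gives no share, gap or SD, so this cannot be shown. The gain runs from almost nothing to substantial.
- **That every quantitative outcome is affected.** Only GA at delivery was modelled. Nothing in the SAP shows that plurality drives the others, and serial measurements have a separate method.

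The objection does not remove the asymmetry: in the scenarios examined the stratified test never had lower power than the unstratified one, and it gained materially when multifetal pregnancies were common.

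**Conclusion.** The point holds as a free improvement for GA at delivery. The SAP prescribes an unstratified test for a named Aim 1 outcome while admitting women on a baseline factor that can be expected to affect that outcome strongly. The consequence is lost precision only. Under the skewed model (172 per arm, within-type SD about 1.7 weeks, 2.7-week gap, 0.55-week effect) the gain in power is about 2 points at 2% multifetal, 3 at 5%, 6 at 10% and 13 at 20%. The share, gap, SD and effect are all assumptions, and the multifetal share matters most. The conclusion that stratifying is worthwhile does not depend on knowing it, because the cost is negligible even when the share is low.

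**What to change.** In section 8, name the Mann-Whitney test stratified by plurality (van Elteren; strata singleton and multifetal) as the between-arm test for GA at delivery. Beside it, report the plurality-adjusted mean difference with 95% CI from a linear model with arm and plurality. State that the stratified rank test is the test and the linear model supplies the estimate, since the two differ in power when GA is skewed.

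Limit the change to GA at delivery and any other mother-level outcome with a single value per woman that the team expects to depend on plurality, and list those outcomes. Stating the expected multifetal share would let readers judge the gain. The SAP names SPSS 22.0 and Epi-info, so the team should confirm that the stratified test can be run there, or name another package.

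The cost is a sentence or two in the SAP and a few lines of code. No extra patients are needed, and plurality is already assessed for eligibility.

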As an open label study, we hope the results of this study will generate robust data that will be used to inform the design equipped to design of a larger national study. Moreover, based on the findings of previous published literature, we predict that expression of sFlt-1, VEGF and PIGF will be significantly altered in pre-eclamptic patients. The design of this study will help determine and validate the clinical utility of the aforementioned biomarker in routine practice for the prediction of PET and disease severity. The use of metformin is expected to reduce the anticipated effects of sFlt-1 as an antiangiogenic factor, therefore, reducing the incidence of

PET and indeed improving maternal and neonatal outcomes and quality of life, reducing hospital admissions and cost of care and better utilization of health care system resources.

This collaborative study involves investigators (scientists and clinicians) from the PHCC, HGH, Women's Hospital [name] and Sidra. Such a cross-disciplinary approach will provide an opportunity for training future scientist in the field of women's health. The more junior members of the team will have the opportunity to be trained on translational research design, and clinical trial management and thereby enhancing the research capacity which both are aligned with Qatar national health strategy. The women hospital will be better catered with enhanced research skills. Pregnant women are usually excluded from clinical trial; however, an advantage of this trial is the safety the intervention (metformin) and thereby increasing public engagement with research and awareness of its importance and benefits.

Evaluation criteria for this study are patient recruitment, quality and consistency of the data and safety of the intervention. Further, the percentage women who developed PET in each arm as well as changes in the studied biomarkers will be quantified and accepting the null hypothesis.

10. Plans for disseminating research results

Once the project is funded, the study team will initiate monthly meetings to discuss study plans and patient recruitment. Team leaders will also meet monthly to share study updates. Furthermore, the study results will be shared among peers in the department through presentation of study findings. Finally, once the study is completed we aim to present our finding at the [name] Medical Corporation Annual Research Day, local and international conferences and in peer-reviewed journals.

11. Future plans

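### The planned biomarker comparison never adjusts for the baseline value, does not name the contrast that tests metformin, and lists within-arm tests that cannot show a metformin effect

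*SAP*

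**What the plan says.** Section 3, Aim 2, second objective, compares the PlGF/sFlt-1 ratio between women on metformin and women on standard care. Section 7(a) collects "study biomarkers of LFT, serum creatinine, sFlt-1, VEGF and PIGF" at baseline, in weeks 11+0 to 13+6. Sections 5 and 7 repeat the biomarkers in the second and third trimesters and at or after delivery.

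For the analysis, Section 8 says that "outcomes measured at different time points should be statistically analyzed both within and between groups using repeated measure ANOVA statistical method", followed by multiple comparison tests. The sentence before it assigns quantitative data between arms to an unpaired t test or a Mann-Whitney test. Section 8 adds "All P values presented will be two-tailed" and "P values <0.05 will be considered as statistically significant". Section 9 makes it an evaluation criterion that "changes in the studied biomarkers will be quantified".

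The only covariate-adjusted model in the SAP is the logistic regression for pre-eclampsia. No sentence gives the baseline biomarker value a role in a biomarker analysis, and none says whether the group main effect, the group-by-time term or a single-visit comparison is the test of metformin.

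**The concern.** Three things are left in a poor state for Aim 2.

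- **Baseline is not used as a covariate.** The trial collects a baseline value, and a woman's later values are likely to be correlated with it. Leaving it out wastes precision that costs nothing to recover.
- **The deciding contrast is not named.** A two-group repeated-measures ANOVA yields several P values that bear on the arms, and the t test or Mann-Whitney test yields more. They have very different power, and the choice among them is left open until the data are seen.
- **Within-arm tests are listed with no limit on their use.** They compare an arm with its own earlier values. Any drift with gestation shows up as change in both arms, so a P value below 0.05 in one arm and above it in the other is not evidence for metformin. Nothing in the SAP rules out reading it that way.

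At stake is a real effect of metformin on the ratio being missed, or one being claimed from the wrong test. The comparison of pre-eclampsia incidence is not affected.

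**Working it through.** **The SAP's own figure.** Section 6 sizes the trial for pre-eclampsia, not for a biomarker: "We expect that for a study power of 80% and to detect a reduction at a level of 5% significance", with rates of "3% versus 11.3% respectively, OR 0.24, 95% CI 0.10 – 0.61", gives "172 patients in each arm, for a total of 344 in both group based on 1:1 ratio". With p̄ = (0.113 + 0.03)/2 = 0.0715 and difference 0.083:

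n = [1.96·√(2·0.0715·0.9285) + 0.8416·√(0.113·0.887 + 0.03·0.97)]² / 0.083² = 150.1, so 151 per arm.

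The continuity correction raises this to 174, close to the stated 172. There is no biomarker power figure to reproduce, so only relative efficiencies can be checked.

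**Inputs.** Two-sided 5% (Section 8). m = 3 later samples (Section 5, Collected data: second trimester, third trimester, after delivery), with m = 2 as the alternative because the opening of Section 7 lists only baseline and the two trimester visits. Assumed, because the SAP does not give them: equal variances (set to 1), equal correlation ρ between all visits, a constant effect δ after baseline, and a baseline sample drawn before the first dose.

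**Variance per woman and effect estimated:**

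- Baseline-adjusted post-baseline mean (ANCOVA): effect δ, variance (1+(m−1)ρ)/m − ρ².
- ANOVA group main effect, baseline as a level of time: effect δ·m/(m+1), variance (1+mρ)/(m+1).
- Change contrast within group-by-time: effect δ, variance (1+(m−1)ρ)/m + 1 − 2ρ.
- Unadjusted t test on the post-baseline mean: effect δ, variance (1+(m−1)ρ)/m.

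Information is effect² divided by variance. At m = 3, ρ = 0.5, with δ = 1:

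- ANCOVA: 1/(0.6667 − 0.25) = 2.4
- Main effect: 0.75²/0.625 = 0.9, so 0.9/2.4 = 0.375 is kept
- Change contrast: 1/0.6667 = 1.5, so 0.625 is kept
- t test: 1/0.6667 = 1.5, so 0.625 is kept

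**Information kept relative to ANCOVA, m = 3:**

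| Test | ρ = 0.3 | ρ = 0.5 | ρ = 0.7 |
|---|---|---|---|
| Group main effect | 0.525 | 0.375 | 0.225 |
| Change contrast | 0.475 | 0.625 | 0.775 |
| t test, post-baseline mean | 0.831 | 0.625 | 0.388 |

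The main-effect row already includes the dilution of the effect to 3/4. The first two rows sum to 1 at every ρ. This is an identity under these assumptions: m²/[(m+1)(1+mρ)] + m/[(m+1)(1−ρ)] = m/[(1−ρ)(1+mρ)]. So one of the two ANOVA tests always loses at least half. They cross at ρ = 0.33, the main effect being the worse one above that value and the change contrast below it.

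If baseline is kept out of the time factor, the ANOVA group effect is the comparison of post-baseline means, and the third row applies.

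**Power.** Take 172 per arm and a δ that ANCOVA detects with 80% power:

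| Test | ρ = 0.3 | ρ = 0.5 | ρ = 0.7 |
|---|---|---|---|
| Group main effect | 53% | 40% | 26% |
| Change contrast | 49% | 60% | 69% |
| 3-df group-by-time test | 34% | 43% | 52% |
| t test, post-baseline mean | 72% | 60% | 41% |

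**Sensitivity.**

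- With m = 2, at ρ = 0.3, 0.5, 0.7, the losses are 53%, 67%, 80% (main effect, diluted to 2/3), 47%, 33%, 20% (change contrast) and 14%, 33%, 58% (t test).
- With m = 3 and correlation that decays as a power of visit distance, adjacent-visit values of 0.3, 0.5, 0.7 give losses of 32%, 43%, 59% (main effect), 61%, 49%, 33% (change contrast) and 4%, 14%, 35% (t test).

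**The case against.** The strongest reply is that the SAP is brief rather than wrong. Section 8 does not say that baseline is a level of the time factor or that the group main effect is the test of metformin. A reader might infer both, since within-group change needs a starting value, and conclude that the metformin effect will be diluted. The text implies the first and is silent on the second. Group-by-time from the same ANOVA is not diluted.

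A reader might also infer that within-arm testing takes the place of the arm comparison. It does not: the same sentence plans analysis between groups, and the t test or Mann-Whitney test is a further between-arm route. Claiming an effect because one arm changed and the other did not is a risk left open, not a stated rule.

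A reader might infer that over half the information will be lost. That depends on ρ, on the effect read and on the correlation pattern, none of which the SAP fixes. The t test on the post-baseline mean loses more than half only above ρ of about 0.61 (m = 3).

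Finally, omitting baseline does not bias a randomised between-arm test, and the SAP sets no power target for the biomarkers.

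All of this stands, and it limits the claim. It does not remove the point: under these assumptions no planned route recovers the information in the baseline value, and the choice among routes is unstated.

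**Conclusion.** The concern holds in a limited form. Section 8 plans no baseline adjustment for the biomarkers, names no deciding contrast, and lists within-arm tests without saying that they cannot support a treatment claim.

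Under equal correlation of 0.3 to 0.7, three later samples and a constant effect after baseline, the loss against baseline-adjusted analysis is about 22% to 78% for the ANOVA tests and 17% to 61% for the unadjusted t test. If correlation decays between visits, the loss is smaller for the main effect and the t test and larger for the change contrast. Dilution to three quarters is conditional on reading the group main effect with baseline as a level of time.

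The consequence is lost precision and an open choice of test for Aim 2, not bias in the randomised comparison. The change should be made. Confidence is medium, because ρ and the intended ANOVA term are not in the SAP.

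**What to change.** Replace the repeated-measures sentence in Section 8, as far as it covers the biomarkers, with the following:

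- Model the post-baseline values by ANCOVA or a linear mixed model, with the PlGF/sFlt-1 ratio on the log scale. Include randomised arm, visit, arm-by-visit and the woman's own baseline value as a covariate.
- Name one between-arm contrast from that model (which visit, or which average over visits) as the only basis for a claim about metformin.
- Report within-arm changes descriptively, without P values.
- Gestational age at sampling may be added as a covariate for the scheduled second- and third-trimester visits only. For samples at delivery or at admission for pre-eclampsia, timing is itself a result of what happened after randomisation, and Section 3 lists gestational age at delivery as an outcome.

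The cost is SAP wording, slightly more analysis work and the loss of the within-arm P values. The baseline and later biomarker values are already to be collected, so no further women or samples are needed.
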